6.2.7 Cumulative Analogue Joint Involvement Scale (CAJIS)

Range of motion across the whole body will also be assessed using the CAJIS.

The assessments will be performed on 12 joints (shoulder, elbow, wrist, hip, knee, and ankle on both the right and left sides), and three body regions (jaw, cervical spine [neck], and thoracic/lumbar spine). Each joint/region will be scored as: 0 = uninvolved; 1 = partially involved; and 2 = ankylosed/completely involved.

The CAJIS Total score will be calculated as the sum of the scores of all joints/regions and ranges from 0 (no involvement) to 30 (maximally involved).

The CAJIS Upper Extremities subscore will be calculated as the sum of the scores from six joints (shoulder, elbow, and wrist on both the right and left sides) and one region (cervical spine [neck]) and ranges from 0 (no involvement) to 14 (maximally involved).

The CAJIS Mobility subscore will be calculated as the sum of scores from six joints (hip, knee, and ankle on both the right and left sides) and ranges from 0 (no involvement) to 12 (maximally involved).

The CAJIS Total score, CAJIS Upper Extremities subscore, and CAJIS Mobility subscore and changes from baseline will be summarized at each scheduled visit with descriptive statistics. Similar summaries will be provided for subgroups defined by presence of new HO at any post-baseline visit (new HO, no new HO).

6.2.8 Global Assessment of Movement

Flare-up movement compared to baseline will be assessed by the subject (or parent proxy) and Investigator. Assessment results will be summarized at each scheduled visit with counts and percentages of flare-ups. Similar summaries will be provided for subgroups defined by presence of new HO at any post-baseline visit (new HO, no new HO).

6.2.9 FOP-Physical Function Questionnaire (FOP-PFQ)

Age-appropriate forms of the FOP-PFQ will be administered to subjects (or parent proxy). The adult form will be administered to subjects 15 years and older. For subjects between 8 and 14 years of age, both the pediatric self-completed and the pediatric proxy-completed forms will be administered. The proxy-completed form will be used for analyses unless only the self-completed form is available.

The FOP-PFQ consists of 28 questions on the adult form and 26 questions on the pediatric form scored on a scale from 1 to 5, with lower scores indicating more difficulty. The questions are described in detail in Appendices 7A, 7B, and 7C of the protocol.

The Total score will be calculated as:

- The sum of the scores from each question and ranges from $28 \times 1 = 28$ to $28 \times 5 = 140$ for the adult form.

- The sum of the scores from each question and ranges from $26 \times 1 = 26$ to $26 \times 5 = 130$ for the pediatric form.

The Upper Extremities subscore will be calculated as:

- The sum of the scores from 15 questions (questions 1, 2, 3, 4, 5, 6, 7, 8, 9, 10, 11, 12, 14, 25, and 26) and ranges from $15 \times 1 = 15$ to $15 \times 5 = 75$ for the adult form.
- The sum of the scores from 18 questions (questions 1, 2, 6, 7, 8, 9, 10, 11, 16, 17, 18, 19, 21, 22, 23, 24, 25, and 26) and ranges from $18 \times 1 = 18$ to $18 \times 5 = 90$ for the pediatric form.

The Mobility subscore will be calculated as:

- The sum of the scores from 13 questions (questions 13, 15, 16, 17, 18, 19, 20, 21, 22, 23, 24, 27, and 28) and ranges from $13 \times 1 = 13$ to $13 \times 5 = 65$ for the adult form.
- The sum of the scores from 8 questions (questions 3, 4, 5, 12, 13, 14, 15, and 20) and ranges from $8 \times 1 = 8$ to $8 \times 5 = 40$ for the pediatric form.

The Total score, Upper Extremities subscore, and Mobility subscore are defined based on information from PROMIS and Hays et al (2013)² for the adult form and a medical review of the questions for the pediatric form.

If a subject is missing some (but not more than 20%) of the contributing question scores, the Total score, Upper Extremities subscore, or Mobility subscore will be calculated as the average observed score multiplied by the number of expected question scores. For example, the Total score would be calculated as the average of the non-missing scores $\times 28$ for the adult form. The determination for sufficient non-missing scores will be made independently for the Total score, Upper Extremities subscore, and Mobility subscore.

As the analysis for FOP-PFQ will be performed across all subjects (adult and pediatric) and the number of contributing questions differs, the scores will be transformed to reflect a percentage of worst score. The percentage of worst score ranges from 0% to 100% with 0% indicating the best possible function and 100% indicating the worst possible function. Table 2 illustrates some sample derivations of the percentage of worst score.

Table 2. Sample Derivations for the Percentage of Worst Score for the FOP-PFQ

Sample Subject	Observed FOP-PFQ Score	Lowest Possible Score	Highest Possible Score	Range of Possible Scores	Distance = Highest - Observed	Distance/Range	Percentage of Worst Score
1	45	15	75	60	30	0.500	50.0%
2	40	15	75	60	35	0.583	58.3%
3	35	15	75	60	40	0.667	66.7%
4	30	15	75	60	45	0.750	75.0%
5	25	15	75	60	50	0.833	83.3%

Percentage of worst scores and changes from baseline will be summarized at each scheduled visit with descriptive statistics. Similar summaries will be provided for the percentage of worst Mobility Subscore for the subgroup of subjects with flare-ups in lower extremities and for the percentage of worst Upper Extremity Subscore for the subgroup of subjects with flare-ups in the upper extremities.

Note that flare-ups in the lower extremities include the following flare-up locations reported by the Investigator: abdomen, ankle or foot, distal lower extremities, hip, knee, lower back, and lumbar spine. Flare-ups in the upper extremities include the following flare-up locations reported by the Investigator: chest, cervical spine, head, jaw, distal upper extremities, elbow, shoulder, wrist or hand, thoracic spine, and upper back.

Similar summaries will be provided for subgroups defined by presence of new HO at any post-baseline visit (new HO, no new HO).

6.2.10 PROMIS Global Health

An age-appropriate form of the PROMIS Global Health short form will be administered to subjects (or parent proxy). The adult form will be administered to subjects 15 years and older. For subjects between 8 and 14 years of age, both the pediatric self-completed and the pediatric proxy-completed forms will be administered. The proxy-completed form will be used for analysis unless only the self-completed form is available.

The PROMIS Global Health short form consists of 10 questions on the adult form and nine questions on the pediatric form scored on varying scales. The questions are described in detail in Appendices 8A, 8B, and 8C of the protocol.

For the adult form, Global Physical Health and Global Mental Health scores will be calculated. The Global Physical Health score will be calculated as the sum of scores from questions 3, 6, 7, and 8, and will range from 4 (worse health) to 20 (better health). The Global Mental Health score will be calculated as the sum of scores from questions 2, 4, 5, and 10, and will range from 4 (worse health) to 20 (better health). In the calculation of the Global Physical Health and Global Mental Health scores, the following questions will be rescaled as shown in Table 3.

Table 3. Rescaled PROMIS Global Health Scale Scores

Question(s)	Score	Rescaled Score
7	0	5
	1-3	4
	4-6	3
	7-9	2
	10	1
8 and 10	1	5
	2	4
	3	3
	4	2
	5	1

If a subject is missing any of the contributing scores, the Global Physical Health or Global Mental Health score will not be calculated.

For the pediatric form, only a Total score will be calculated as the sum of scores from the first seven questions and will range from 7 (worse health) to 35 (better health). If a subject is missing some (but not more than three) of the contributing question scores, the Total score will be calculated as the average observed score multiplied by the number of expected question scores. For example, the Total score would be calculated as the average of the non-missing scores x 7.

Global Physical Health and Global Mental Health scores and Total scores will be converted to T-scores for analysis as described in detail in [Appendix 1](#). A T-score of 50 is normal and increments of 10 +/- 1 standard deviation away from the norm. A T-score <50 indicates worse health, while a T-score >50 indicates better health. Note that higher values indicate better health.

T-scores and changes from baseline will be summarized at each scheduled visit with descriptive statistics. Data from adult and pediatric forms will be summarized separately. Similar summaries will be provided for subgroups defined by presence of new HO at any post-baseline visit (new HO, no new HO).

6.2.11 Flare-up Pain and Swelling

Adults and pediatric subjects 8 years and older will rate the pain associated with their flare-ups using a numeric rating scale (NRS) from 0 (no pain) to 10 (worst pain ever experienced). Pediatric subjects less than 9 years old will rate pain using the Faces Pain Scale – Revised (FPS-R), which ranges from 0 (no pain) to 10 (very much pain) in 2-point increments. Swelling associated with flare-ups will be rated on a scale from 0 (no swelling) to 10 (worst swelling ever experienced).

Ratings for pain and swelling and changes from baseline will be summarized at each scheduled visit with descriptive statistics.

6.2.12 Assistive Devices and Adaptations for Daily Living

Subjects will be given a list of FOP assistive devices and adaptations grouped into 12 categories and asked to select those they use for daily living.

The use of assistive devices and adaptations will be summarized overall and by category at each scheduled visit with counts and percentages of flare-ups. The number of devices and adaptations used will be summarized overall and by category at each scheduled visit with descriptive statistics.

The use of new-onset assistive devices and adaptations will be summarized overall and by category with counts and percentages of flare-ups. New-onset assistive devices and adaptations are defined as assistive devices and adaptations used at a post-baseline visit that were not used at baseline.

6.2.13 Bone, Cartilage, Angiogenesis, and Inflammation Biomarkers

Blood and urine samples will be collected for cartilage, bone, angiogenesis, and inflammation. Bone and cartilage biomarkers include osteocalcin, bone specific alkaline phosphatase (B-ALP), procollagen type I C-terminal propeptide (PICP), procollagen 1 N-terminal propeptide (PINP), CD retinoic acid-sensitive protein (CD-RAP), and C-terminal telopeptide (CTX). The angiogenesis biomarker is the ratio of fibroblast growth factor and urine creatinine. Inflammation biomarkers include erythrocyte sedimentation rate (ESR), C reactive protein (CRP), interleukin 6 (IL-6), interleukin 1 beta (IL-1 beta), tumor necrosis factor (TNF), creatine kinase (CK), and lactate dehydrogenase (LDH).

Biomarkers values and changes from baseline will be summarized at each scheduled visit with descriptive statistics. Note that results obtained locally rather than from the central laboratory will not be used to calculate change from baseline and will be excluded from these summaries. Results captured as “<” or “>” will be rounded up or down accordingly for analysis (eg, “<0.61” will be rounded to 0.60).

Abnormal values at baseline and new-onset abnormal values post-baseline will be summarized with counts and percentages of flare-ups. New-onset abnormal values are defined as values from biomarkers that were normal at baseline and abnormal post-baseline or were abnormal at baseline and abnormal in the opposite direction post-baseline (eg, abnormal low at baseline and abnormal high post-baseline). Note that results obtained locally will be included in these summaries.

The following figures will be generated (note that the unit of analysis is each flare-up):

- Mean biomarker values over time (one figure per biomarker, each figure with one line).
- Mean biomarker values over time by incidence of new HO (one figure per biomarker, each figure with one distinctive line per subgroup [new HO, no new HO]).
- Mean biomarker values over time by baseline edema status (one figure per biomarker, each figure with one distinctive line per subgroup [baseline edema present, baseline edema not present]).

- Biomarker values over time by flare-up (one figure per biomarker, each figure with one distinctive line per flare-up). Flare-ups will be identified in the legend with subject ID, flare-up identifier (eg, Flare A, Flare B), gender, and age.
- Mean percent of normal high biomarker values over time (one figure per biomarker, each figure with one line). Percent of normal high = $100 \times \text{value} / \text{upper limit of normal range}$.
- Mean percent of normal high biomarker values over time by incidence of new HO (one figure per biomarker, each figure with one distinctive line per subgroup [new HO, no new HO]).
- Mean percent of normal high biomarker values over time by baseline edema status (one figure per biomarker, each figure with one distinctive line per subgroup [baseline edema present, baseline edema not present]).
- Percent of normal biomarker values over time by flare-up (one figure per biomarker, each figure with one distinctive line per flare-up). Flare-ups will be identified in the legend with subject ID, flare-up identifier, gender, and age.

6.2.14 Duration of Active Symptomatic Flare-up

Subjects will keep a daily diary during the Flare-up Component where the question “Is your flare-up ongoing today?” is answered. Subjects with at least 80% of diary data (at least 67 days with non-missing data) will be used for analysis.

The number of symptomatic days will be calculated as the number of days where the diary question is answered “Yes”. The number of symptomatic days will be summarized with descriptive statistics.

The status of the flare-up will be determined at Week 12 and EOT. If there are no symptomatic days recorded in the diary, the flare-up will be considered “Resolved prior to the first dose of study drug”. If the last symptomatic day recorded in the diary is on or before the specified visit and is followed by at least one asymptomatic day (ie, diary question is answered “No”), the flare-up will be considered “Resolved”. If the last symptomatic day recorded is on the last diary entry, the flare-up will be considered “Not resolved”. The status of the flare-up will be summarized at Week 12 and EOT with counts and percentages of flare-ups.

The days to flare-up resolution will be calculated as follows:

- If the flare-up was considered “Resolved prior to the first dose of study drug”, days to flare-up resolution = 0.
- If the flare-up was considered “Resolved”, days to flare-up resolution = date of flare-up resolution – date of first dose + 1, where the date of flare-up resolution is the last symptomatic day.
- If the flare-up was considered “Not resolved”, days to flare-up resolution = date of last diary entry – date of first dose + 1.

The days to flare-up resolution will be summarized with descriptive statistics.

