2.4 Study Treatment

Subjects in the Adult Cohort were scheduled to be treated with 5 mg palovarotene daily for up to 24 months (non-flare-up based treatment); however, some adult subjects chose not to receive non-flare-up based treatment.

Flare-up based treatment will begin as soon as possible after a subject reports onset of a flare-up and the flare-up has been confirmed by the Investigator. In the event of an eligible flare-up, subjects in the Adult Cohort will receive open-label palovarotene treatment as follows:

- 20 mg for 28 days. The first dose will be taken upon flare-up confirmation by the Investigator.
- 10 mg for 56 days, for a total flare-up treatment duration of 84 days; treatment may be extended if the flare-up is ongoing and continue until the flare-up resolves. Dosing will be extended in 4-week intervals and be based on clinical signs and symptoms as assessed by the Investigator.

Subjects not receiving non-flare-up based dosing will only be treated during eligible flare-ups and will receive weight-adjusted doses of 20 and 10 mg palovarotene as follows:

Weight Range Category	20-mg Equivalent	15-mg Equivalent	10-mg Equivalent	7.5-mg Equivalent*	5-mg Equivalent*
20 to <40 kg	12.5 mg	10 mg	6 mg	4 mg	3 mg
40 to <60 kg	15 mg	12.5 mg	7.5 mg	5 mg	4 mg
≥60 kg	20 mg	15 mg	10 mg	7.5 mg	5 mg

* In the event of dose de-escalation.

If the subject experiences intolerable side effects during flare-up based dosing, the dose may be reduced to the next lower dose; if the subject is already receiving the lowest possible dose, then study drug will be discontinued. Treatment may be extended after the 84-day treatment period (flare-up based dosing) if the flare-up is ongoing and continue until the flare-up resolves. Dosing will be extended in 4-week intervals based on clinical signs and symptoms as assessed by the Investigator, with remote visits performed every 2 weeks while on treatment. In the event the subject requires dose de-escalation due to an intolerable side effect for a previous flare-up, then the dose the subject will receive for a subsequent flare-up will be determined by the Investigator and the Medical Monitor.

After the Flare-up Day 84/EOT visit has been conducted and the flare-up is considered resolved, subjects in the Adult Cohort will resume the non-flare-up based treatment.

Subjects not receiving non-flare-up based dosing who do not experience an eligible flare-up will not be treated.

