3.2 Handling of Dropouts or Missing Data

As there is no effective treatment for subjects with FOP, it is assumed they will be highly motivated to adhere to the protocol and treatment visits. Thus, it is expected that there will be minimal missing data, and most subjects will complete the study. The efficacy analysis will be performed using observed data only. Missing efficacy data will not be imputed.

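### The symptomatic-day count treats unanswered diary days as symptom-free, and in Part B the 80% / 67-day completeness rule fits only an 84-day diary

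*SAP*

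**What the plan says.** Both SAPs have subjects answer a daily diary question on whether the flare-up is still ongoing (Part A 7.2.13, Part B 6.2.14). The entry rule is the same in both: "Subjects with at least 80% of diary data (at least 67 days with non-missing data) will be used for analysis". The summary is then a plain count: "The number of symptomatic days will be calculated as the number of days where the diary question is answered" Yes. It is reported with descriptive statistics. Neither section says how an unanswered day is treated.

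The same section of the Part B SAP defines a second measure from calendar dates. For a resolved flare-up, "days to flare-up resolution = date of flare-up resolution – date of first dose + 1, where the date of flare-up resolution is the last symptomatic day".

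On flare-up length, Part B Section 2.4 gives "10 mg for 56 days, for a total flare-up treatment duration of 84 days; treatment may be extended if the flare-up is ongoing", and "Dosing will be extended in 4-week intervals and be based on clinical signs and symptoms as assessed by the Investigator". Diary-based status is read beyond the standard period as well: "The status of the flare-up will be determined at Week 12 and EOT". The general missing-data rule in Part B Section 3.2 is "Missing efficacy data will not be imputed".

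For the FOP-PFQ (Part B 6.2.9), where up to 20% of items may also be missing, the score is "calculated as the average observed score multiplied by the number of expected question scores".

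**The concern.** A symptomatic day can be recorded only on a day with an entry. A raw Yes count over an incomplete diary gives a blank and a No the same value, so the error runs in one direction: gaps can lower the count but never raise it. The rule not to impute efficacy data does not cure this, because adding up only the Yes entries scores every gap as zero. Where the SAP sums questionnaire items with a similar tolerance for missingness, it rescales the sum. Here it does not.

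The second problem is the threshold. The sentence is carried over unchanged from Part A, where the Flare-up Component ends at Flare-up Day 84 (Part A Section 5). In Part B, treatment can be extended and status is read at end of treatment, so the percentage and the day count can give different answers for the same diary.

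At stake is a descriptive summary of a listed secondary endpoint (Part B 6.2, item 10), shown for PVO 20/10 mg and Prior Non-Flare-up/PVO 20/10 mg. If diary completeness differed between those groups, the counts would differ for that reason alone.

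**Working it through.** **The plan's own figure.** Inputs: an 84-day diary (Part B 2.4) and an 80% rule (6.2.14). 0.80 × 84 = 67.2, so 67 is 80% rounded to the nearest day (67/84 = 79.8%). Strictly, at least 80% needs 68. The one-day difference has no practical consequence, but it shows that 67 was derived from 84 days.

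**Loss in an 84-day diary with 67 answers.** Unanswered days: 84 − 67 = 17, and 17/84 = 20.2%. Let S be the true number of symptomatic days.

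- Every day symptomatic (S = 84): counted 67, a loss of 17/84 = 20.2%.
- Gaps at random: expected count S × 67/84. For S = 42 this is 33.5, again 20.2% low.
- All 17 gaps on symptomatic days: counted S − 17. For S = 42, 25 (17/42 = 40% lost). For S = 30, 13 (17/30 = 57% lost). For S of 17 or less, 0, and the section would then class the flare-up as resolved before first dose.
- All 17 gaps after resolution: counted S, no loss.

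**The date-based measure.** In a simulation with S = 42 consecutive symptomatic days from first dose and 17 random gaps in 84 days, the mean Yes count was 33.5 and the mean days to resolution 41.8. Random gaps before the last Yes do not shorten the date-based measure.

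**Extended flare-ups in Part B.** With 28-day extensions, diary length D is 112 or 140 days if the diary runs to end of treatment.

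| D (days) | Answers needed for 80% | Unanswered at that minimum | Unanswered if 67 is fixed |
|---|---|---|---|
| 84 | 68 (0.80 × 84 = 67.2) | 16/84 = 19.0% | 17/84 = 20.2% |
| 112 | 90 (0.80 × 112 = 89.6) | 22/112 = 19.6% | 45/112 = 40.2% |
| 140 | 112 (0.80 × 140) | 28/140 = 20.0% | 73/140 = 52.1% |

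A 112-day diary with 70 answers passes the 67-day test and fails the 80% test (70/112 = 62.5%). A programmer cannot satisfy both.

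**Check on the obvious correction.** Proration is Yes days / answered days × diary days. Take 30 Yes, then 37 No, then 17 blank days after resolution. The raw count of 30 is right; proration gives 30/67 × 84 = 37.6, which is 25% too high. The percentage of answered days carries the same assumption (30/67 = 44.8% against a true 30/84 = 35.7%). Neither should stand alone. The raw count and the count with blanks taken as symptomatic (30 + 17 = 47) bracket the truth.

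**The case against.** The strongest reply is that the endpoint is duration, listed with a start date and an end date, and that days to flare-up resolution matches it better and is robust to gaps before the last Yes. The count is only a companion description. This stands, and it limits the point to the number of symptomatic days. A reader might infer that flare-up duration as such is understated; the documents do not support that.

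A reader might also take 20% as a ceiling. It is the largest unanswered share in an admitted 84-day diary. The relative loss in the count can be larger or zero, depending on where the gaps fall.

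A reader might further conclude that extended flare-ups are understated by 40% or more. That needs two readings the SAP does not settle: that 67 is a fixed minimum rather than a gloss on 80%, and that the diary continues past Day 84. Part B ties the diary to a Flare-up Component that it does not define. Reading status at end of treatment suggests continuation but does not state it. What is established is the conflict between the two parts of the rule.

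Finally, it is tempting to say the bias flatters palovarotene. Part B compares palovarotene groups with each other (Section 9), uses no statistical modelling (Section 3.1), and has no untreated diary group. Nothing shows that completeness differs between the groups.

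The objection that FOP-PFQ proration is a weak model is fair: those are items at one visit, whereas a symptom course is ordered in time. It argues against proration as the main fix, not against correcting the count.

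**Conclusion.** The point holds for the number of symptomatic days in both SAPs. Followed as written, the rule gives a count that is biased low whenever a symptomatic day goes unanswered. At the minimum of 67 answers in 84 days, the loss is 20.2% if all days were symptomatic, or in expectation with random gaps. Actual diary completeness is not given in the documents, so the size of the bias in the trial is unknown.

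In Part B there is also an internal conflict in the completeness criterion for any diary longer than 84 days. If 67 is fixed and the diary runs to end of treatment, the unanswered share can reach 40.2% at 112 days and 52.1% at 140. If 80% is scaled to diary length, it stays at or below 20%.

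This does not touch the primary endpoint and leaves days to resolution largely intact. It is worth correcting because the present rule yields a biased summary and the correction is cheap.

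**What to change.** - In both SAPs, report symptomatic days as a percentage of answered diary days alongside the raw count.
- Add a sensitivity summary that counts unanswered days as symptomatic. With the raw count it bounds the effect of gaps.
- Use simple proration, if at all, only as a further sensitivity labelled as assuming random gaps.
- In Part B, state when the diary ends for an extended flare-up, and apply the 80% rule to each flare-up's actual diary length instead of a fixed 67 days (90 of 112, 112 of 140).

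The cost is SAP wording and one or two derived variables. A few extended flare-ups with sparse diaries may drop out of the summary.
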